2. OBJECTIVES

Primary study objective:

To study effectivity of the epidural injection with analgesic and anti-inflammatory medication to relieve the symptoms within two weeks follow up.

It will be evaluated what the average leg pain score is in both treatment arms at two weeks follow up. It will be evaluated how long the effect lasts.

The leg pain and functionality at 4 weeks after randomization will also be evaluated to get informed on the responsiveness on TEI in a somewhat later stage.

Secondary study objectives:

To evaluate the outcome of TEI in the first two weeks after randomization as a predictor of NRS leg pain at 14-16 and ca 26 weeks after onset of leg pain.

Ideally, responsiveness to TEI can predict the clinical condition at 14-16 weeks after onset of sciatica. The hypothesis is that being non-responsive to TEI within two weeks, predicts an unsatisfactory condition after 14-16 weeks of suffering. This is the category of patients that in contemporary care in the Netherlands will be offered a surgical intervention. If our hypothesis is correct, in the future, this population of patients can be offered a surgical intervention at an earlier time point.

The ca 26-week time point is chosen since in the Sciatica trial [2], both the conservative and the surgical group demonstrated comparable outcome data.

Patients in this study are included while suffering from severe leg pain for 3-8 weeks.

Presumably most patients will enter the study with 4-6 weeks of leg pain. This means that on average 10 weeks after randomization, the 14-16 week leg pain time point is reached. This means that 21 weeks after randomization the ca 26-week leg pain time point is reached.

The response in NRS leg pain, ODI and patient satisfaction at 1 week after injection and at 2 weeks after injection will be correlated to the value of these parameters at 10 and 21 weeks after randomisation.

To evaluate the cost-effectivity of analgesic/anti-inflammatory epidural injections to relieve symptoms of early sciatica.

A substantial portion of the patients in this study will eventually have an MRI of the lumbar spine. These MRIs will be evaluated according to our standard MRI evaluation protocol, that has been proven to generate additional successful conclusions and subsequent publications in the past [10-15]. Protruding disc, disc and vertebral end plate changes (MODIC) will be correlated to clinical data.

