A portion of the patients in this study will eventually be operated. Disc material from these patients will be evaluated for the presence (and type) of macrophages and these data will be correlated to MRI and clinical data. These additional outcome measures can be combined with the research lines on etiology of sciatica that are executed in the Neurosurgery Department of the LUMC [16].

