Costs (Cost intervention, health care use, and loss of productivity): Cost diaries will be filled out at 10 and 21 weeks after randomisation. Health care utilization (including physiotherapy, visits to GP and specialists, nursing care and medication), patient costs, and absenteeism will be measured using cost diaries filled out by the patient.

Complications: Post-TEI exacerbation of NRS leg pain (>1 point additional leg pain) that lasts for at least 24 hours will be documented as a clinically relevant complication of TEI. Other rare adverse events from treatment with TEI such as pain at site of injection, persisting numbness, vasovagal reaction, accidental discal puncture, accidental dural puncture or headache will be recorded as well.

Radiological parameters: the level of disc herniation, the size and shape of disc herniation, disc degeneration (Pfirrmann scale), vertebral end plate changes, and facet degeneration (Weishaupt scale) will be evaluated by two independent researchers, blinded to clinical and histological data, on T2 weighted sagittal and transversal MRI.

Histology: During surgery, the herniated disc material will be collected and fixed in 4% formaldehyde solution. For evaluation, the tissue will be subsequently embedded in paraffin blocks. These blocks will be stained with Hematoxylin and used for general macrophage staining (CD68), and subtype macrophage staining: M1(iNOS & CD40) and M2 (Arg1 & CD163), T cell staining (CD45-RO) and B cell staining (CD20). Furthermore, presence of Propionibacterium Acnes and Staphylococcus Epidermidis will be verified by PCR analysis for 16S rDNA. Positive samples will be gram stained for further identification of the bacteria.

All histological data will be quantified by two independent researchers, blinded to clinical and MRI data, and an inter-agreement analysis will be conducted.

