6.1.3 Other study parameters

Data with respect to the following variables will be collected at baseline:

- Demographic data;
- Age, gender, length, weight, BMI, tobacco exposure, alcohol abuse;
- History of previous radicular symptoms in the legs;
- Usage of pain medication.

Data with respect to the following items will be collected concerning TEI:

- Timing of administration (days after randomization);
- Number of injections and timing of those;
- NRS leg pain after injection;
- Other complications.

Data during follow up will be collected:

- If an MRI is performed: MRI data;
- If surgery is performed: disc material for histology.

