8.3 Other study parameters

MRI: the level of disc herniation on MRI will be compared to the clinical diagnosis (made before MRI) and the percentage of clinical diagnosis prediction success can be calculated.

The size and shape of disc herniation, disc degeneration (Pfirrmann scale), vertebral end plate changes, and facet degeneration (Weishaupt scale) will be correlated to baseline clinical data using t-tests.

Histology: the number of M1 and M2 macrophages will be correlated to NRS leg pain and ODI at all time points using t-tests and mixed models analysis.

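### Section 6.1.2 names only T2-weighted images for reading end plate (Modic) changes; paired sagittal T1 and T2 series are needed to score them by type and to avoid missing changes isointense on T2

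*Combined protocol and SAP*

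**What the plan says.** The radiological parameters are described in section 6.1.2. After herniation level, size and shape, the list continues: "disc degeneration (Pfirrmann scale), vertebral end plate changes, and facet degeneration (Weishaupt scale) will be evaluated by two independent researchers". The same sentence sets the reading conditions for the whole list: the items "will be evaluated by two independent researchers, blinded to clinical and histological data, on T2 weighted sagittal and transversal MRI". Disc degeneration and facet degeneration each have a named scale. End plate changes have none.

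Section 2 identifies the end plate changes and gives their purpose: "Protruding disc, disc and vertebral end plate changes (MODIC) will be correlated to clinical data". It also says, of the scans, "These MRIs will be evaluated according to our standard MRI evaluation protocol". That protocol is cited through earlier publications, but its content and sequences are not given.

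Section 8.3 gives the analysis: "vertebral end plate changes, and facet degeneration (Weishaupt scale) will be correlated to baseline clinical data using t-tests". Section 6.1.3 makes the data conditional: "If an MRI is performed: MRI data". For patients who are operated on, section 2 plans to examine disc material for the "presence (and type) of macrophages and these data will be correlated to MRI and clinical data".

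**The concern.** One reading instruction is applied to items that need different images. The sequence named suits the disc and herniation items. It is a poor basis for an item that section 2 labels with the Modic name, because that scale is defined on two sequences. If the readers follow section 6.1.2 literally, they cannot assign a type reliably, and even a present/absent score may be incomplete.

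What is at stake is the quality of one imaging variable. It is to be related to clinical data and, through the histology plan in section 2, may also be set against macrophage findings. The blinded double reading is the natural time to settle how the variable is scored. Adding the type later would mean reopening the scans and repeating the reading.

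**Working it through.** The plan gives no figure on this point, so there is none to reproduce. The check sets the sections side by side.

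**Step 1: what is read, and on which images.** Section 6.1.2 has a single sentence covering herniation level, herniation size and shape, disc degeneration, end plate changes and facet degeneration. All are tied to T2-weighted sagittal and transversal images. T1 does not appear anywhere in the document.

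**Step 2: what the variable is.** Section 2 attaches the Modic label. Neither section 6.1.2 nor section 8.3 says whether it is scored as present/absent, by type or by extent.

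**Step 3: what the scale requires.** The standard definition, taken here as a premise because the documents do not state it, is:

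| Modic type | T1 signal | T2 signal |
|---|---|---|
| 1 | low | high |
| 2 | high | iso- to high |
| 3 | low | low |

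Two things follow from the T2 column alone:

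- A bright end plate on T2 fits type 1 or type 2. The column that separates them is T1.
- A type 2 change that is isointense on T2 does not stand out from unaffected marrow on T2. It can be scored as absent, although it is bright on T1. A present/absent variable is therefore also affected.

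**Step 4: what the analysis asks for.** Section 8.3 uses t-tests against baseline clinical data. A t-test compares two groups, which fits a present/absent split. No contrast by type is stated in section 2, 6.1.2 or 8.3.

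**Step 5: who contributes data.** Section 6.1.3 collects MRI data only where a scan is made. The documents do not give the number of patients expected to have one, or how often each Modic type occurs. No size of misclassification or loss of precision can be calculated from them.

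**The case against.** The strongest reply has three parts.

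- **Section 6.1.2 names T2 but does not exclude other series.** Section 2 defers to a standard MRI evaluation protocol, which may already include T1. This stands as a reason not to claim that the reading will be on T2 alone. It does not remove the point: section 6.1.2 is the only reading instruction in the document, and if the standard protocol does use T1, section 6.1.2 is incomplete and should say so.

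- **No analysis by Modic type is planned, so typing is an added wish.** It is true that none is planned, and presence or absence could still be correlated as written. The reply is incomplete, because a change isointense on T2 can be missed in a present/absent score as well.

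- **The scans are kept and could be re-read later.** This is fair, and it limits the harm. It would still mean a second reading.

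A reader might go further and infer that the plan forfeits the inflammatory Modic type, and that its Modic associations are biased towards zero by a known amount. The documents do not support this. They never mention a Modic type or call one inflammatory. The one cited report that links Modic changes with disc inflammation refers, in its title, to Modic changes as a whole. If types 1 and 2 were pooled and only type 1 were related to pain, the observed difference would be the type 1 share times the true difference. Shares of 25%, 50% and 75% would then leave 25%, 50% and 75% of it. Both the shares and the type-1-only effect would be assumptions, and the result merely repeats the share put in. Relative to its own question, a present/absent contrast is not diluted by pooling types.

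**Conclusion.** The point holds as a limited weakness in a stated method. Section 6.1.2 names T2-weighted images as the basis for reading end plate changes that section 2 calls Modic changes. On the standard definition of that scale, those images cannot reliably separate types 1 and 2 and can miss changes isointense on T2. A paired T1 and T2 reading gives a better variable, whether it is then used by type or as present/absent.

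The effect is confined to an exploratory parameter in the patients who have an MRI. The primary comparison of leg pain at two weeks and the sample size are untouched. The size of the effect on the Modic correlation cannot be stated from the documents.

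The conclusion rests on two assumptions: that the Modic scale is used in its standard form, and that the readers follow section 6.1.2 as written. If the standard MRI protocol already prescribes T1, the remaining defect is that section 6.1.2 does not reflect it.

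**What to change.** In section 6.1.2:

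- Keep T2 for herniation level, size and shape, the Pfirrmann grade and the Weishaupt grade.
- State that end plate (Modic) changes are read on paired sagittal T1 and T2 series of the same scan and scored by type (0/1/2/3).
- Where no T1 series exists, record only present/absent and leave the patient out of any analysis by type.

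If the standard MRI evaluation protocol already says this, a reference to it in section 6.1.2 with the sequences named is enough. If the score is then analysed by type, section 8.3 should say which groups are compared, because a t-test takes two groups and the score has four levels.

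The cost is a sentence or two of text and one more existing series to open per scan, with no extra scan and no extra reader. The downside is that some scans will lack T1 and drop to present/absent. Those readings keep the risk of missing changes isointense on T2, so their number should be reported.

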6.1.3 Other study parameters

Data with respect to the following variables will be collected at baseline:

- Demographic data;
- Age, gender, length, weight, BMI, tobacco exposure, alcohol abuse;
- History of previous radicular symptoms in the legs;
- Usage of pain medication.

Data with respect to the following items will be collected concerning TEI:

- Timing of administration (days after randomization);
- Number of injections and timing of those;
- NRS leg pain after injection;
- Other complications.

Data during follow up will be collected:

- If an MRI is performed: MRI data;
- If surgery is performed: disc material for histology.

6.2 Randomisation, blinding and treatment allocation

Randomisation will take place using block randomisation in a 1:1 allocation ratio in order to obtain equal study groups. When the patient is enrolled, a randomization envelope will be opened to determine patient allocation. Since this is an open-label randomized controlled trial allocation is not concealed.

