3. STUDY DESIGN

This is a prospective, open-label, randomized controlled trial on patients suffering from acute sciatica (3-8 weeks pain in the leg with a NRS ≥ 6) (see inclusion and exclusion criteria) in which consecutive patients who meet the inclusion criteria are invited to participate in the trial. The trial will take place at the Spaarne Gasthuis Hospital (SG) in Hoofddorp and Haarlem, the Netherlands in cooperation with researchers from Leiden University Medical Center (LUMC), Leiden, the Netherlands. Patient recruitment will occur at GP practices (GP collective Haarlemmermeer and Kennemerland, 185 GP's). The GP will diagnose the patient and, if the patient is diagnosed with sciatica, refer to the study investigator.

Eligible patients that are willing to participate are randomized to treatment with transforaminal epidural injections (treatment group) or standard conservative care (control group).

Randomization will take place using block randomization in a 1:1 allocation ratio. Patients from the treatment group will be treated with TEI, oral pain medication and, if deemed necessary by the GP, physiotherapy. The control group will only receive oral pain medication and if deemed necessary additional physiotherapy. For this study, the control group will not include placebo injections since we want to compare treatment with injections to treatment without injections. The focus will not be on the type of medication that is contained in the injection. Furthermore, a control group without injections will demonstrate what percentage of patients will experience spontaneous relief of symptoms (only using medication and/or physiotherapy) as it is known that in a significant part of the patients sciatica resolves without any intervention.

At baseline, clinical and demographic data are gathered for patients in both groups. Patients from the treatment group will receive TEI within 4 days after randomization. Patients from this group can receive multiple injections but an injection is only repeated after a certain interval time according to usual anaesthesiological guidelines. For all injections, details on timing, frequency and prevailing complications will be gathered.

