4. STUDY POPULATION

4.1 Population (base)

Patients suffering from sciatica that visit the general practitioner (GP collective Haarlemmermeer (60 GP) and Kennemerland (125 GP) referring to the Spaarne Gasthuis location Haarlem and location Hoofddorp (adherence 750.000 patients) are evaluated to be candidates for this study. If the general practitioner diagnoses a lumbar radicular syndrome (LRS) (sciatica) with an NRS leg pain of 6 points or more on a 10 points scale, and the duration of pain is longer than 3 weeks and shorter than 8 weeks, the patients are offered to participate in the RCT. If they are willing to consider participating in the RCT, the GP will send the contact details to the study investigator. Patients will be offered at least 48 hours to decide whether they want to be enrolled in the study. The study investigator will contact the patients and explain the study again. If patients are deciding to cooperate, informed consent will be signed. If patients are randomized to continue usual care, the GP will be informed and he/she will conduct conservative treatment as deemed suitable. If the patient is randomized to TEI, the patient is referred to the anaesthesiologist to receive TEI. TEI treatment will be received within 4 days.

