4.3 Exclusion criteria

A potential subject who meets any of the following criteria will be excluded from participation in this study:

- Age under 18 years;
- Condition preventing to receive TEI (for instance, allergy for lidocaine);
- Severe scoliosis;
- TEI received in 6 months before randomization date;
- Surgery for sciatica at the same level;
- Surgery for sciatica at another level within one year before inclusion;

- Pregnancy.

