6.3 Study procedures

Patients that are diagnosed by the GP with acute sciatica (3-8 weeks after onset of pain, NRS \geq 6) that meet in- and exclusion criteria will be offered the study. If patients are willing to be randomized, they will be contacted by the study investigator. The study investigator will inform the patients again and checks whether patients have access to e-mail. This is done to make sure that they can fill in the questionnaires online (a web-based database with questionnaires is used for data collection (Castor, LUMC)). The study investigator will ask for informed consent. Randomization will take place. If patients are randomized to the intervention group, they will be sent to the anaesthesiologist and planned for TEI within 4 days after randomization without visiting the neurologist. If patients are randomized to the

control group, they will receive oral pain medication according to the care of the general practitioner.

The patient will be invited to the hospital where baseline data will be gathered and questionnaires will be filled in. During this contact the study investigator will guide the patient through the online questionnaire fill-in procedure to get the patient accustomed with this procedure.

Questionnaires will be filled in after 1, 2, 4, 10 and 21 weeks after randomization for both the control group and TEI group.

If leg pain remains severe after the 2 weeks after randomization primary endpoint, patients can be referred to the neurologist if the general practitioner deems it necessary. Patients can be offered surgery if applicable.

If an MRI is made during the process, MRI data will be gathered as mentioned above.

If a lumbar discectomy is performed, disc tissue will be gathered during surgery and analysed as mentioned above.

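### The plan does not say that block sizes vary or are withheld, and it disclaims concealment, so upcoming assignments may be predictable to the person who recruits

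*Combined protocol and SAP*

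**What the plan says.** Section 3 gives the method as "Randomization will take place using block randomization in a 1:1 allocation ratio", and section 6.2 repeats it: "Randomisation will take place using block randomisation in a 1:1 allocation ratio in order to obtain equal study groups". Neither section gives a block size, says that sizes vary or are withheld, names strata, or says who generates and holds the list.

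On the mechanism, section 6.2 says: "When the patient is enrolled, a randomization envelope will be opened to determine patient allocation". It does not describe the envelopes as sealed, opaque or numbered. It then adds: "Since this is an open-label randomized controlled trial allocation is not concealed".

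On who recruits, section 4.1 says: "The study investigator will contact the patients and explain the study again". Section 6.3 puts consent directly before allocation: "The study investigator will ask for informed consent. Randomization will take place". Section 6.3 describes the hospital contact for baseline data after the randomisation step, whereas section 10.1 places baseline data collection during inclusion. The web-based system is named in sections 6.3 and 10.1 for data collection only.

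**The concern.** Two separate protections keep a recruiter from knowing the next assignment. One is concealment: the assignment cannot be read before it is issued. The other is unpredictability: it cannot be deduced from those already issued. Section 6.2 disclaims the first, on the ground that the trial is open-label, and is silent on the second. Open-label status concerns what is known after allocation. It is not a reason to forgo concealment before allocation.

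The two need separate remedies. In an open-label trial past assignments become visible. If the block size is constant and can be inferred, the rest of a block is known as soon as one arm's quota is used up, however well the envelope is sealed.

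What is at stake is comparability at entry. The primary outcome is patient-reported leg pain (section 6.1.1), compared by an unpaired t-test with no baseline adjustment stated (section 8.1). If the choice or timing of whom to enrol depended on the expected arm, this analysis would not correct for it.

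**Working it through.** **Inputs.** From the plan: 1:1 blocks (sections 3 and 6.2); difference 1.5, SD 2.6, power 90%, significance level 5%, 10% loss, 142 patients (section 4.4). Assumed, because the plan gives no block size: constant sizes of 4, 6 and 8, known to or inferable by the recruiter, who also sees past assignments.

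**The plan's own figure.** With a two-sided 5% level, n per group = 2 × (1.960 + 1.282)² × 2.6² / 1.5² = 63.1, rounded up to 64, as stated. The total is 128, and 128 / 0.90 = 142.2, against the stated 142 (143 if rounded up). The sample size is not in question; 142 serves only as the denominator below.

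**Assignments certain in advance.** In a block of size 2b with b per arm, the expected number of places left once one arm is used up is 2b/(b+1), so the certain share is 1/(b+1). As a check with b = 2, the orders AABB, ABAB and ABBA (and their mirror images) leave 2, 1 and 1 certain places. The mean is 4/3 out of 4, which is 1/3.

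**Best-guess accuracy.** Guessing the arm that is behind within the block is correct in a share [b + (4^b / C(2b,b) − 1)/2] / (2b) of cases:

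- b = 2: [2 + (16/6 − 1)/2] / 4 = 0.708
- b = 3: [3 + (64/20 − 1)/2] / 6 = 0.683
- b = 4: [4 + (256/70 − 1)/2] / 8 = 0.666

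| Assumed constant size | Certain share | Of 142 | Best guess |
|---|---|---|---|
| 4 | 1/3 = 33.3% | 47 | 70.8% |
| 6 | 1/4 = 25.0% | 36 | 68.3% |
| 8 | 1/5 = 20.0% | 28 | 66.6% |

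The counts ignore the incomplete last block (142 is not a multiple of 4, 6 or 8); allowing for it lowers them by about one patient. Without blocking, the best guess is right 50% of the time and nothing is certain.

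**After the change.** Lists of 142 were simulated with sizes drawn at random. The observer knows the set of possible sizes, but not the block boundaries, and tracks every block state consistent with the history.

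- Sizes 4 and 6: certain share about 5.4% (about 8 patients), best guess 69%.
- Sizes 4, 6 and 8: certain share about 2.3% (0.023 × 142 ≈ 3 patients), best guess 68%.

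Varying the size therefore removes nearly all the certain assignments and leaves the best-guess advantage almost where it was.

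**The case against.** The strongest case on the other side has four parts.

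*The block size is unknown.* Leaving it out of a protocol is good practice, and varying, withheld sizes may already be in use. This stands. The percentages are conditional on a constant size that can be inferred, and a statement that sizes vary and are withheld would answer that half of the point. It would not answer the sentence that disclaims concealment.

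*The route to steering is not documented.* A reader might infer that the study investigator applies the judgement-based exclusion criteria and sees every assignment. The text does not say so. Under sections 4.1, 6.3 and 9.2 the GP diagnoses, and patients who meet the criteria are offered the study before the investigator contacts them. Nothing says that the 185 GPs see the running sequence. Who opens the envelopes and how many people recruit at the two locations are not stated. Delaying contact is also bounded by the limit of 8 weeks of pain. What remains is the investigator's documented role in contacting and consenting patients in an open-label trial.

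*The consequence cannot be quantified.* A reader might convert best-guess accuracy into a bias and a raised type I error. That needs an assumed prognostic difference, and it needs every guess to be acted on; the documents support neither. Best-guess accuracy also barely moves under the change, so such figures would not measure its benefit. None is given here.

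*The disclaimer may be loose wording.* The sentence on concealment may mean only that the arm is known once assigned. That is plausible, and it is why a reader should not infer that staff can see forthcoming assignments. As written, though, it gives up a protection that an open-label trial can and should keep.

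**Conclusion.** The point holds as a weakness in the stated method. The plan specifies 1:1 blocks and an envelope, disclaims concealment, and does not say that sizes vary or are withheld. If the size is constant and inferable, one fifth to one third of assignments (28 to 47 of 142 for sizes 8 to 4) are certain in advance. These figures rest on the assumed sizes and on a recruiter who sees past assignments, which is a reasonable inference from the open-label design and the investigator's role but is not stated. The documents do not show that enrolment has been or would be steered, and they do not support a figure for bias or type I error. The gain on offer is removal of near-certain assignments and of an unconcealed envelope. It is worth taking because it is cheap.

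**What to change.** In section 6.2, with matching words in section 3:

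- Specify randomly permuted blocks of randomly varying size, 1:1. Have the list generated by someone outside the recruiting team, and keep the sizes out of the protocol and unknown to recruiters.
- Replace the envelope and the sentence saying that allocation is not concealed. Release each assignment only after eligibility, consent and baseline scores are recorded, through the web-based data system if it supports this, otherwise from an independently held list. State separately that treatment is open-label once assigned.
- State who confirms eligibility at that step and who requests the assignment.

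If varying, withheld sizes are already in use, saying so is enough for that part. If recruitment has begun, the change needs a new list for patients not yet randomised.

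The cost is a few sentences, the list, and recording baseline scores before the assignment is released. No patients or procedures are added and the sample size is unchanged. Final group sizes may differ by a few patients: with sizes up to 8, an unfinished last block can leave a difference of at most 4.

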8. STATISTICAL ANALYSIS

8.1 Primary study parameter(s)

The study data will be analysed according to the intention-to –treat principle. The mean NRS for leg pain will be compared between the two groups using the unpaired t-test. This will also be done at the 4-week time point.

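### Section 6.2 gives up allocation concealment because the trial is open-label, which is not a valid reason, and no readable section says how the envelopes are secured

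*Combined protocol and SAP*

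**What the plan says.** Section 6.2 specifies block randomisation at 1:1 and describes the mechanism in one sentence: "When the patient is enrolled, a randomization envelope will be opened to determine patient allocation". It then adds: "Since this is an open-label randomized controlled trial allocation is not concealed". Section 3 repeats the blocks, the ratio and the open-label design, without further detail on the sequence or its custody.

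The route into the trial is as follows.

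- Section 3: "consecutive patients who meet the inclusion criteria are invited to participate in the trial".
- Section 4.1: the GP makes the diagnosis and applies the pain and duration criteria. For patients willing to consider the trial, "the GP will send the contact details to the study investigator". Then: "Patients will be offered at least 48 hours to decide whether they want to be enrolled in the study". And: "The study investigator will contact the patients and explain the study again".
- Section 6.3: "The study investigator will ask for informed consent. Randomization will take place".

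The primary analysis in 8.1 is unadjusted: "The mean NRS for leg pain will be compared between the two groups using the unpaired t-test".

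**The concern.** The sentence in 6.2 treats two separate safeguards as one. Blinding protects the trial after assignment, and a comparison of injection with no injection, without placebo, cannot blind the patient. Concealment protects the trial before assignment: whoever decides whether and when a patient enters must not know which arm comes next. Nothing in an open-label design rules that out, so the reason given does not support the rule.

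What is at stake is comparability of the arms. If the person explaining the trial and taking consent knows or can foresee the next assignment, then encouragement, timing or the decision to proceed can depend on it, even without intent. The arms could then differ in expected 2-week leg pain for reasons other than treatment. The unadjusted t-test in 8.1 would carry such a difference straight into the estimate.

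**Working it through.** **1. Does any other section repair the sentence?** Envelopes are mentioned only in 6.2. Against the usual elements of concealment, the readable text gives:

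| Element | Where described |
|---|---|
| Envelope opened at enrolment | 6.2 |
| Consent before randomisation | 6.3 |
| Sealed, opaque or sequentially numbered | nowhere |
| Who generates the list, and who prepares, holds or opens the envelopes | nowhere |
| Block size, and whether it is kept from recruiting staff | nowhere |

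**2. Do the guards that are described close the gap?** Inviting consecutive patients fixes who is approached. It does not fix who enrols or in what order, because patients have at least 48 hours to decide and the investigator speaks to them again before consent. Opening the envelope at enrolment protects only if its content could not be known or foreseen earlier.

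**3. Why blocks matter here.** Past allocations are visible in an open-label trial. If a fixed block size b were known to the recruiter, the share of allocations that are certain in advance is 1/(b/2 + 1). For b = 4, the fourth is always certain, and the third is certain when the first two agree (probability 1/3), so the share is (1 + 1/3)/4 = 33%. Sizes 2, 6, 8 and 10 give 50%, 25%, 20% and 17%. The plan states no block size, so these values are assumed. They show only why block sizes should be kept from recruiting staff.

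**4. Sensitivity of the primary test.** Inputs from section 4.4: SD 2.6, 64 per group, target difference 1.5, 5% significance. The plan does not state sidedness; two-sided is assumed.

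- SE = 2.6 × √(2/64) = 0.460. Critical t on 126 df = 1.979.
- Check on the plan's own figure: noncentrality 1.5/0.460 = 3.26 gives power 89.9%, matching the stated 90%.
- With no true effect and an imbalance b in expected 2-week NRS, the type I error is P(|T| > 1.979), where T is noncentral t with noncentrality b/0.460.
- For b = 0.3: noncentrality 0.3/0.460 = 0.65. The two tails are 9.5% and 0.5%, giving 9.9% in total.

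| Assumed imbalance (NRS points) | Type I error |
|---|---|
| 0 | 5.0% |
| 0.1 | 5.5% |
| 0.2 | 7.2% |
| 0.3 | 9.9% |
| 0.4 | 13.9% |
| 0.5 | 19.1% |

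An imbalance of 0.3 is 0.3/1.5 = 20% of the target difference. These figures would apply to any unadjusted t-test with this standard error, whatever the source of the imbalance. They do not measure the effect of the wording in 6.2.

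**The case against.** The strongest reply is that this is a wording fault. The heading of 6.2 promises a statement on blinding, and the disputed sentence is the only one that can serve as it. The sentence before it has an envelope opened at enrolment to determine the allocation, which has little purpose if the allocation is already known. Section 6.3 puts consent before randomisation, and section 4.1 has the GP apply the main entry criteria before referral. Read together, the intended meaning may well be that treatment is not blinded.

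That reading is plausible, and it limits what can be claimed about conduct. It does not remove the point. On that reading the protocol misstates its own design and concealment is left undescribed; on the literal reading a safeguard is given up without cause. Either way the sentence needs replacing.

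A second reply is that the detail may sit elsewhere. Section 10.2 refers to an institutional standard protocol and a monitoring plan to be written later. Neither is available to us and neither is said to cover envelopes. This is a reason not to infer practice from silence, but it does not correct a rule stated in 6.2.

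A third reply is that the imbalances are assumed. This stands in full, and the severity does not rest on them.

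**Conclusion.** The rule in 6.2 is wrong as written and should be corrected. This is more than missing detail, because the text states that allocation is not concealed and gives a reason that does not hold. The size of any bias cannot be derived, since neither envelope handling nor any selection effect is given. The figure of about 10% type I error rests on an assumed imbalance of 0.3 points, the plan's SD and group size, and a two-sided test.

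A reader might infer three stronger things, none of which the documents support.

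- That recruiting staff could in fact see the sequence, or that enrolment was steered. The text does not show this, and an envelope opened at enrolment after consent points towards some concealment having been intended.
- That the type I error of this trial is 10%. Nothing links envelope handling to 0.3 points or to any other value.
- That baseline questionnaires are completed after allocation is known, from the narrative order in 6.3. Section 10.1 places baseline collection at inclusion, and the flow diagram, which is not shown to us, may settle the order. That is a separate matter and forms no part of this point.

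**What to change.** In 6.2, replace the sentence on concealment with:

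> Treatment is not blinded. The next allocation is concealed from recruiting staff until eligibility and consent are recorded, using a web-based system or sequentially numbered, opaque, sealed envelopes prepared and held by someone not involved in recruitment; block sizes are not disclosed to recruiting staff.

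If recruitment has already run, document how the envelopes were actually prepared, held and opened, since the written record otherwise says that allocation was not concealed.

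The cost is one replaced sentence and, if envelopes are kept, an existing staff member outside recruitment to prepare and hold them. No extra patients or data items are needed. No change to 8.1 is asked for: baseline adjustment is a separate choice and would address only measured factors.
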